10.3.3.3 Change from baseline to Month 6 in plasma globotriaosylceramide

This endpoint will be analyzed using the mFAS. All available data will be used regardless of occurrence of ICEs such as premature treatment discontinuation or changes in background medication.

Missing data will be imputed applying an MI approach assuming MAR. The imputation model includes the baseline value, the two stratification factors (sex and ERT treatment status at screening), all post-baseline monthly scores up to Month 6 and treatment group.

The MAR assumption can be considered reasonable for this endpoint as it is an objective assessment and not subject-reported and therefore less likely to be related to reasons for study withdrawal. In addition, subjects, site staff as well as the sponsor are blinded to the plasma Gb3 results until after database lock and a lower amount of missing data is expected compared to the abdominal pain and stool consistency endpoints.

After imputation, the analysis will be performed using an ANCOVA as described in Section [10.3.2.2](#).

A two-sided 95% CI will be calculated for the difference in the mean changes from baseline to Month 6 between lucerastat and placebo.

To explore the robustness of inferences from the main analysis described above to deviations from its underlying assumptions regarding the nature of missing data, control-based MI assuming MNAR using the CR (described in section [10.3.2.2](#)) and J2R approaches (described in section [10.3.2.4](#)) will be applied.

A supportive analysis using an MMRM approach will be conducted to characterize the treatment effect over time such that change in plasma Gb3 will be analyzed on all available data from all monthly visits without replacement of missing values.

The model will enable:

- Estimation of the treatment difference (lucerastat minus placebo) in the mean changes from baseline to Month 6 along with the corresponding 95% CI;
- Characterization of the patterns of change over time in the mean change from baseline in Gb3 by treatment group.

10.3.4 Analysis of other efficacy variables

The analyses of all other efficacy variables will be described in detail in the SAP. Other variables may also be analyzed by subgroups. Other efficacy endpoints will be analyzed at each relevant time point listed in the visit and assessment schedule [see [Table 5](#) and [Table 6](#)] along with any data from unscheduled visits as appropriate.

10.3.5 Analysis of the safety variables

The SAF will be used to perform all safety analyses.

If not otherwise stated, only treatment-emergent safety data will be considered in tables and figures. All safety data will be included in listings, with flags for safety data not considered to be treatment-emergent.

10.3.5.1 Adverse events

10.3.5.1.1 Treatment-emergent adverse events and serious adverse events

Treatment-emergent AEs and SAEs will be tabulated by study treatment, system organ class (SOC) and preferred terms within each SOC: the number and percentage of subjects who experienced at least one (S)AE, at least one (S)AE within each SOC and at least one (S)AE within each preferred term will be displayed. (S)AEs will also be summarized by decreasing frequency of preferred term. (S)AEs will also be tabulated by maximum intensity and relationship to lucerastat or placebo.

10.3.5.1.2 Adverse events leading to premature discontinuation of study drug

(S)AEs leading to premature discontinuation of study drug will be summarized in a similar manner as that described in Section [10.3.5.1.1](#).

10.3.5.2 Vital signs

Descriptive summary statistics by visit and study treatment will be provided for observed treatment-emergent values and absolute changes from baseline in HR, SBP, DBP, MAP and body weight.

Treatment-emergent notable blood pressure abnormalities will also be summarized descriptively.

10.3.5.3 Electrocardiography

Descriptive summary statistics by visit and study treatment will be provided for observed treatment-emergent values and absolute changes from baseline in numeric 12-lead ECG values (HR, PR, QRS, QT, QTcB, and QTcF).

Changes in 12-lead ECG variables (HR, PR, QRS, QT, QTcB, and QTcF) from pre-dose to 2 h and 4 h post dose will be summarized at the Month 1 visit.

Treatment-emergent marked abnormalities for 12-lead ECG variables (HR, PR, QRS, QT, QTcB, and QTcF) will be summarized at all visits and pre/post-dose time points.

In addition, summaries of treatment-emergent morphological ECG abnormalities that were not present before first study treatment intake (using data from the ECG provider) will be provided.

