After single dosing of lucerastat (range: 100–4000 mg) in healthy subjects, peak plasma drug concentrations were attained between 0.5 and 4.0 h, and the apparent terminal elimination half-life ($t_{1/2}$) ranged from 3.6–16.9 h. Following repeated administration of lucerastat (range: 200–1000 mg b.i.d.), peak plasma concentration observed during the dosing interval were attained between 0.5 h and 4.0 h. The PK of lucerastat were proportional for the area under the plasma concentration-time curve (AUC) extrapolated to infinity ($AUC_{0-\infty}$) over the dose range tested after both single and multiple dosing. There was no relevant increase in exposure from Day 1 to Day 7, indicating absence of accumulation over time. The time to reach steady state was approximately 2 days.

Renal clearance of unchanged lucerastat varied from 68–85% of oral clearance and mean renal excretion of unchanged lucerastat per daily dose from 68–85%. No clinically relevant food effect was observed.

The PK results of 1000 mg b.i.d. obtained in subjects with FD were in line with those observed in healthy subjects. The PK profiles of lucerastat were similar in subjects with

mild renal function impairment when compared with healthy subjects. Plasma lucerastat concentrations were higher in subjects with moderate and severe renal function impairment. The $t_{1/2}$ was longer in subjects with moderate (9.6 h) or severe renal function impairment (16.1 h) than in healthy subjects (7.0 h). Overall, this resulted in a 1.6- and 3.2-fold increase in $AUC_{0-\infty}$ of lucerastat in subjects with moderate and severe renal function impairment, respectively, when compared with healthy subjects.

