7.2.3.3 Weight and height

Height will be measured without shoes at screening.

Body weight will be measured in indoor clothing but without shoes at screening and each visit thereafter.

Body weight and height data will be recorded in the eCRF.

7.2.3.4 *Electrocardiogram assessment*

A standard pre-dose 12-lead ECG will be performed at all scheduled visits. At the Month 1 visit, 2 additional 12-lead ECGs will be performed 2 h and 4 h after study treatment administration.

A re-test may be performed if the result for an ECG is missing or to repeat an abnormal ECG. A re-test does not need to be reported as an unscheduled visit [see Section 7.1.2].

ECGs will be performed with the subject in a fully rested supine position after the subject has been allowed to rest for a minimum of 5 minutes prior to the measurement. The date and exact clock time of ECGs will be entered in the eCRF.

A central ECG vendor (see ECG manual for contact details) will be used for the evaluation of all protocol-mandated ECGs, including re-tests due to ECG abnormalities and ECGs performed at unscheduled visits. The site personnel will electronically transmit the ECGs to the central ECG vendor for central reading.

The following variables will be evaluated by the central ECG vendor: HR (bpm), PR (ms), QRS (ms), QT (ms), QTc according to Bazett's formula (QTcB) (ms), QTcF (ms) and any ECG findings. QTc (ms) will be calculated according to Bazett's and Fridericia's formula ($QTcB = QT/[RR]^{1/2}$ and $QTcF = QT/[RR]^{1/3}$, respectively).

ECG reports will be provided by the central ECG vendor to the investigator/delegate. If specific (pre-defined in the ECG manual) ECG abnormalities are observed, the central ECG vendor will alert the sponsor and the site personnel.

All ECG reports must be reviewed, signed and dated by the investigator or delegate within 10 working days of receipt and filed with the source documentation. The investigator/delegate must indicate on the ECG report whether abnormal values or findings are considered clinically relevant or not. Clinically relevant ECG findings that are known at the time of signing of the ICF must be recorded in the medical history or FD forms of the eCRF. Any clinically relevant ECG abnormalities detected after signing of the ICF must be reported as an AE or SAE as appropriate [see Section 9], and must be followed until the finding returns to normal, is considered stable, or until the change is no longer clinically relevant.

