## **10 SAFETY VARIABLES**

For determination of treatment-emergent events, the safety analysis will retain the AEs with an onset date between the start of treatment date (included, provided that AE onset is not prior to first dose of study treatment, i.e., AE.AESTRTPT is different from BEFORE) and EOT + 30 days (included). AEs with missing or incomplete onset date compatible with being between the start of treatment date (included, provided that AE onset is not prior to first dose of study treatment, i.e., AE.AESTRTPT is different from BEFORE) and EOT + 30 days (included) will be considered treatment emergent.

For determination of treatment-emergent events, the safety analysis will retain the laboratory values, vital signs, and ECGs with a sampling or assessment date between the start of treatment date (excluded) and EOT + 30 days (included). The baseline value will be taken as the last value available up to the start of treatment date (included).

All laboratory, vital signs and ECG data are taken into account regardless of whether they correspond to scheduled or unscheduled assessments.

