### 16.4.2 Treatment-emergent marked abnormalities

The number and percentage of subjects with treatment-emergent marked abnormalities will be tabulated by treatment group for each ECG variable. For a given parameter, percentages will be based on the number of subjects at risk: those not meeting the criterion at baseline (or with a missing baseline value) and with at least one post-baseline value (not later than EOT + 30).

Marked abnormalities are classified as high (H, HH, HHH) or low (L, LL) based on values occurring above the higher limit or below the lower limit, respectively. It is possible that, for a given parameter, the same subject is counted as a high marked abnormality for an observed value and as a low marked abnormality for a different observed value. Only the most severe abnormality will be counted (e.g., a subject meeting the “HH” criterion for a specific parameter will not be summarized under “H” for this parameter).

The definitions of marked abnormality used are presented in [Table 20](#).

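### The SAP drops the protocol's breakdown of marked ECG abnormalities by visit and by pre-/post-dose time point, and does not declare the change

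*Protocol*

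**What the plan says.** Protocol 10.3.5.3 names six variables and sets the level of detail: "Treatment-emergent marked abnormalities for 12-lead ECG variables (HR, PR, QRS, QT, QTcB, and QTcF) will be summarized at all visits and pre/post-dose time points."

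SAP 16.4.2 has no such dimension: "The number and percentage of subjects with treatment-emergent marked abnormalities will be tabulated by treatment group for each ECG variable." Subjects are at risk if they did not meet the criterion at baseline (or have no baseline value) and have any later ECG up to EOT + 30 days. High and low are counted separately, and within each "Only the most severe abnormality will be counted". SAP 10 adds: "All laboratory, vital signs and ECG data are taken into account regardless of whether they correspond to scheduled or unscheduled assessments."

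On timing, Protocol 7.2.3.4 schedules a pre-dose ECG at every visit, and at Month 1 "2 additional 12-lead ECGs will be performed 2 h and 4 h after study treatment administration". Protocol 1.2.3 reports that, on repeated dosing, "peak plasma concentration observed during the dosing interval were attained between 0.5 h and 4.0 h".

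SAP 16.4.1 keeps the 2 h and 4 h split for observed values and for change from pre-dose. SAP Table 20 sets criteria for HR, PR, QRS, QTcB and QTcF but not for QT. SAP Section 20 records changes to subgroups only.

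**The concern.** A safety summary specified in the protocol is missing from the SAP, with no declaration and no reason given. What disappears is the number of subjects in each arm above a PR, QRS or QTc limit at the time points closest to peak concentration. In the any-time count, an abnormality at 2 h on drug cannot be told apart from one at trough, or from one recorded weeks after the last dose. If the any-time counts differ between arms, or fail to differ, the reader of the study report cannot tell whether near-peak ECGs are responsible.

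**Working it through.** **Text.** The two plans set side by side:

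| | Protocol 10.3.5.3 | SAP 16.4.1 and 16.4.2 |
|---|---|---|
| Marked abnormalities by visit | yes | no |
| Marked abnormalities at pre-dose, 2 h, 4 h | yes | no |
| Any-time worst-value count | not specified | yes |
| Observed values and changes at 2 h, 4 h | changes | both |
| QT among the categorised variables | yes | no criterion |
| Departure declared in SAP Section 20 | – | no |

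SAP Table 15 does not restore the breakdown. It governs the by-visit summaries of values, and where several ECGs fall on one day it keeps the first available central one. At Month 1 that would normally be the pre-dose ECG.

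**What is pooled.** A completer has four scheduled pre-dose ECGs after baseline (Months 1, 3, 5, 6) and two post-dose ECGs (Month 1). So 4/6, or two thirds, of the scheduled ECGs in the count are at trough. Unscheduled ECGs are added. In early stoppers, so are ECGs from the post-treatment observation period that fall within 30 days of the last dose.

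**Size.** The documents give no ECG abnormality rate, so there is no figure of the plan's own to reproduce. What follows is illustration only. Assume a risk b at each ECG, tripled to 3b at each of the two post-dose ECGs on lucerastat, with all ECGs independent. Take 79 and 39 subjects (SAP Section 2).

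- One post-dose time point: 3b against b.
- Any post-dose ECG (2 h or 4 h): 1 − (1 − 3b)² against 1 − (1 − b)².
- Any-time count: 1 − (1 − b)⁴(1 − 3b)² against 1 − (1 − b)⁶.

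At b = 3%, any post-dose gives 1 − 0.91² = 17.2% against 1 − 0.97² = 5.9%. The any-time count gives 1 − 0.97⁴ × 0.91² = 26.7% against 1 − 0.97⁶ = 16.7%.

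Each cell shows lucerastat against placebo, then difference in points, risk ratio, and power (two-sided 5%, normal approximation):

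| b | One post-dose time point | Any post-dose | Any-time count |
|---|---|---|---|
| 1% | 3.0 v 1.0; 2.0; 3.0; 6% | 5.9 v 2.0; 3.9; 2.97; 12% | 9.6 v 5.9; 3.8; 1.64; 9% |
| 2% | 6.0 v 2.0; 4.0; 3.0; 12% | 11.6 v 4.0; 7.7; 2.94; 24% | 18.5 v 11.4; 7.1; 1.62; 15% |
| 3% | 9.0 v 3.0; 6.0; 3.0; 18% | 17.2 v 5.9; 11.3; 2.91; 37% | 26.7 v 16.7; 10.0; 1.60; 21% |
| 5% | 15.0 v 5.0; 10.0; 3.0; 33% | 27.8 v 9.8; 18.0; 2.85; 62% | 41.2 v 26.5; 14.7; 1.55; 34% |

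No test is planned on these counts; power is only a gauge. Pooling lowers the risk ratio. Against a single time point, though, the pooled difference is larger and the power is no lower. The gain comes from combining 2 h and 4 h.

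**Effect of independence.** Take instead a 2% background and 10 added points at each post-dose ECG. With independence, any post-dose gives 22.6% against 4.0% (18.6 points, ratio 5.7), and the any-time count 28.6% against 11.4% (17.2 points, ratio 2.5). If background abnormalities recur in the same subjects at every ECG, both tables give 0.02 + 0.98 × (1 − 0.9²) = 20.6% against 2.0%, and the dilution vanishes.

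**The case against.** A reader might infer that the SAP hides or loses an effect at peak exposure. The documents do not support this. Every post-dose ECG feeds the any-time count, and the worst value is kept. SAP 16.4.1 summarises observed values and changes at 2 h and 4 h, and SAP 14 prescribes minimum, quartiles and maximum for continuous variables, so an extreme QTc at 2 h appears as the maximum in its arm. Listings of all safety data (Protocol 10.3.5) and alerts from the central ECG vendor (Protocol 7.2.3.4) also remain.

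A reader might also infer that the pooled count is the weaker tool. Against a table of single time points it is not: at b = 3% the difference is 10.0 points pooled against 6.0, and power 21% against 18%.

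Three further points on that side have weight. The protocol gives no reason for the two post-dose ECGs, so a purpose of detecting peak effects is inference, though their timing fits the reported peak. The thorough QT study was negative up to a single dose of 4000 mg, albeit in healthy subjects (Protocol 1.2.3). And Protocol 6.2 and 10.2.3 leave the abnormality criteria to the SAP, so the missing QT row is a minor omission.

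What the objection does not answer is the text. The breakdown was specified, was not carried over, and the change is not recorded. A maximum shows that one subject was extreme; it does not show how many crossed the limit.

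**Conclusion.** The mismatch is certain on the wording of the two documents and needs no assumption. Its consequence is limited: the number of subjects per arm over a threshold at near-peak time points will not be shown, and abnormalities in the any-time count cannot be placed as trough, post-dose or off-drug. How far this would mute a real signal cannot be derived from the documents. The figures above rest on assumed rates and independent ECGs, show a larger effect on the risk ratio than on the absolute difference, and shrink as within-subject correlation rises. No hypothesis test, estimand or primary conclusion is affected. Severity: minor.

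**What to change.** In SAP 16.4.2, add a table of marked ECG abnormalities by treatment group and visit, with Month 1 shown as pre-dose, 2 h, 4 h, and any post-dose (2 h or 4 h combined). Give each row its own denominator: subjects with an ECG at that time who did not meet the criterion at baseline. Keep the any-time count. For uncorrected QT, either add a criterion to Table 20 or state in Section 20 that it is not categorised. If the breakdown is deliberately left out, record that in Section 20 with a reason.

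The cost is one table from data already collected, plus SAP wording. The drawback is small counts. At an assumed 3% rate, about 39 × 0.03 = 1.2 placebo subjects are expected at a single time point, and the chance of none is 0.97³⁹ = 30%. That is the reason for including the combined post-dose row.

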10.3.5.4 Laboratory data

10.3.5.4.1 Changes from baseline in laboratory variables

Descriptive summary statistics by visit and study treatment will be provided for observed treatment-emergent values and absolute and percentage changes from baseline for laboratory tests (hematology, blood chemistry, cardiac enzyme, urinalysis).

Data will be displayed in SI units whenever possible and graphical approaches will be applied for certain variables.

10.3.5.4.2 Treatment-emergent marked laboratory abnormalities

Laboratory abnormalities will be summarized descriptively by study treatment as categorical variables.

10.3.6 Analysis of other variables

A full description of all other analyses will be described in the SAP.

10.4 Interim analyses

No interim analysis is planned for efficacy and/or futility for this study.

10.5 Sample size

The planned sample size for this study is 99 subjects using a 2:1 allocation ratio (66 lucerastat, 33 placebo) and is primarily based on a test for the mean difference between lucerastat and placebo in the change from baseline to Month 6 in the “modified” BPI-SF3 score.

The sample size calculation for the primary endpoint analysis is based on the following assumptions: a clinically relevant difference of 2 points on the 11-point scale (0–10) between lucerastat and placebo, a corresponding SD of 3 points, a two-sided type I error of 5%, and equal group variances. These assumptions come from an expected mean decrease from baseline to Month 6 in BPI-SF3 in the lucerastat group of 1.0-1.5 (2-year data for subjects on ERT; [Hoffmann 2007b]), and an expected mean increase from baseline in the placebo group of approximately 0.5 to 1.0 [Weidemann 2014]. Following these assumptions 99 subjects will provide a power of 87.2% to detect a treatment difference between lucerastat and placebo on the primary endpoint. The calculations were conducted using East 6.5 based on a two-sided t-test for independent samples.

For the analysis of the secondary efficacy endpoints, it is expected that about 70% of the randomized subjects will be included in the mFAS-GIS. Under this assumption the assessment of the secondary endpoints may be carried out on about 69 subjects (approximately 46 on lucerastat and 23 on placebo). Little is known from the literature on the expected effect size that might be observed for these endpoints however a reasonable treatment effect on the abdominal pain endpoint (NRS-11) could be a difference (delta) of

1.5–2.5 points on that scale with an expected variability (SD) in the region of 2.5–3.5. For illustration purposes, and in absence of missing data, the power to detect such an effect with this sample size for the analysis of a continuous endpoint is shown in [Table 7](#).

Table 7 Power to detect a treatment difference for continuous secondary endpoints analyzed on the mFAS-GIS for a range of deltas and SDs (n = 69 subjects)

alpha = 5% two-sided			
delta	SD = 2.5	SD = 3.0	SD = 3.5
1.5	63.9%	48.8%	38.0%
2.0	87.0%	73.0%	59.7%
2.5	97.1%	89.5%	78.7%

SD = standard deviation.

11 DATA HANDLING

11.1 Data collection, data transfer procedure and data access

The investigator/delegate is responsible for ensuring the accuracy, completeness and on time reporting of subject data. All source documents should be completed in a neat, legible manner to ensure accurate interpretation and traceability of the data. Data reported in the eCRF derived from source documents must be consistent with the source documents.

eCRF data will be captured via Electronic Data Capture. The investigator and site personnel will be trained to enter and edit the data via a secure network, with secure access features (username, password, and identification — an electronic password system). A complete electronic audit trail will be maintained. The investigator/delegate will approve the data (i.e., confirm the accuracy of the data recorded) using an electronic signature (ref. to US 21 CFR Part 11).

Entries recorded by the subject in the eDiary are considered source data. All records on the eDiary will be date and time stamped. Each time the subject makes an entry into the eDiary, he/she will be required to enter his/her own confidential password. The eDiary device will transfer data to the eDiary vendor's central server automatically on a nightly basis. The communication software ensures a secure transfer of data by encryption. The data will remain in an encrypted state during transmission to the server. The transfer process is validated to ensure that the data on the central server is an accurate and complete copy of the eDiary data. Once the data are on the central server, the site staff, eDiary vendor, and sponsor representatives can access the data in a view-only mode on a 24 hours per day, 7 days per week basis. This data access is role-based and strictly view-only. Access to the data on the server requires a valid user identification and password combination. Site personnel will review and ensure completeness of the subjects' entries.

For each subject enrolled, regardless of study treatment initiation, an eCRF must be completed and signed by the investigator/delegate. This also applies to those subjects who fail to complete the study.

